1.2 Study design

ENGAGE-DM (ENhancing outcomes through Goal Assessment and Generating Engagement in Diabetes Mellitus) is a pragmatic, prospective, intention-to-treat, randomized controlled trial designed to examine the impact of a novel intervention among patients with T2D that combines behavioral interviewing and shared decision-making delivered by pharmacists over the telephone compared with usual care. After the completion of the trial, we will examine whether a patient's response to the intervention could have been predicted based on their demographics, comorbidities or medication treatment-related factors.

This trial is being conducted among commercially-insured individuals whose medical and prescription benefits are administered by Horizon Blue Cross Blue Shield of New Jersey (Horizon). Horizon is the largest health insurer in New Jersey and administers plans for over 3.8 million beneficiaries.

Following the principles of pragmatic trial design, potentially eligible patients for inclusion in this study were those who: (1) were ≥ 18 years of age, (2) had filled a prescription for 1 or more oral hypoglycemic agents within the prior 12 months, and (3) had evidence of poor glycemic control (A1C $\geq 8\%$) within the previous 6 months, assessed using the most recent HbA1c lab values provided to Horizon Blue Cross Blue Shield. If patients had multiple HbA1c lab values, the latest value was evaluated. An HbA1c threshold of 8% was chosen based on the minimum threshold that nearly all patients should achieve based on guidelines from the American Diabetes Association (ADA); it is also a threshold for major quality measures for health plans. Patients were excluded if, prior to identification, they had fewer than 3 months of continuous enrolment in the health plan, had recently filled insulin (e.g., to exclude patients with type 1 diabetes), or had no available telephone contact information, which would preclude contact for enrolment and delivery of the intervention.

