3. PRIMARY AND SECONDARY VARIABLES

3.1 Primary outcome (mean change in glycemetic control):

The primary outcome of interest will be the pre- to post-intervention change in mean HbA1c levels to the end of the 12-month follow-up period. Follow-up will begin from the date of treatment group assignment. The data for this outcome will be based on laboratory information that Horizon Blue Cross Blue Shield of New Jersey receives from over 200 patient-centered medical homes and other population health programs used for quality improvement monitoring. This laboratory information will be used to measure the change in HbA1c levels at the end of follow-up. In specific, the HbA1c result recorded closest to the 12-month end of follow-up as provided in the laboratory data will be used for the primary analysis.

For subjects with missing outcome data, multiple imputation will be used to impute missing follow-up values to calculate the change in HbA1c levels.¹⁰ Of note, all patients by definition for inclusion in the study will have baseline HbA1c values. This imputation approach is used to generate multiple results for missing values based on the underlying distribution of the available data. We will test the robustness of this approach with sensitivity analyses that use alternative methods of handling missing data, including complete case analysis.

This outcome will be analysed formally. We will also explore any potential differences in effectiveness by the pharmacist delivering the intervention.

3.2 Secondary outcome (proportion achieving glycemic control):

The secondary glycemic outcome will include the proportion of patients achieving optimal glycemic control. Optimal glycemic control will be defined as the proportion of patients who achieved an HbA1c result <8.0% in the 12-month follow-up period. This conservative threshold is based on the minimum threshold that nearly all patients should achieve based on guidelines from the American Diabetes Association (ADA) and quality measures used to assess the performance of health plans.^{11,12} In specific, we will use the laboratory information provided to Horizon and will use the HbA1c result recorded closest to the 12-month end of follow-up for the primary analysis.

For subjects with missing outcome data, we will use multiple imputation to impute missing follow-up values to calculate the proportion of patients who achieved this threshold.

This outcome will be analysed formally.

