4.2 Analysis methods

4.2.1 Primary objective (Effectiveness of intervention):

Baseline characteristics:

We will measure key baseline characteristics in the 12-months prior to randomization in the pharmacy and medical claims data and enrolment files. These characteristics will include sociodemographic characteristics, such as age and sex, which will be measured in the enrolment files. We will also measure baseline clinical characteristics such as the presence of coronary artery disease, chronic obstructive pulmonary disease, asthma, hypertension, hyperlipidemia, congestive heart failure, depression, liver disease, chronic kidney disease, osteoporosis and prior macrovascular complications. These will be measured in medical claims files using ICD-10 codes. We will also measure the type of oral glucose-lowering agent used in the baseline period (e.g., medical class), average PDC at baseline, and whether or not the medication is branded. We will also measure patients' latest copayments for oral glucose-lowering agents in the baseline period. Finally, we will also measure baseline healthcare resource utilization variables as characteristics including the number of days hospitalized and the number of physician office visits.

We will report, in tabular format, the means and frequencies of baseline characteristics prior to assignment separately for patients in the intervention and control groups and compare these values using t-tests, chi-square tests, and their non-parametric analogues, as appropriate. We will provide absolute standardized differences between the two treatment groups.

Primary analyses:

Primary outcome (change in HbA1c): In the primary analysis, the primary outcome, mean change in glycemic control, will be compared using generalized estimating equations with an identity link function (as a continuous variable) and normally distributed errors within the imputed full analysis set, as described above. Data will be presented as the unadjusted absolute difference in the change in HbA1c between the groups along with 95% confidence intervals.

Secondary outcome (proportion achieving glycemic control)

1) *Proportion of patients achieving optimal glycemic control* (defined by HbA1c < 8): This outcome will be compared using generalized estimating equations with a logit link and binary distributed errors. Data will be presented as the unadjusted odds ratio for optimal glycemic control between the groups along with 95% confidence intervals.

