Secondary outcomes (medication adherence):

1) *Mean PDC in each study arm:* This outcome will be compared using generalized estimating equations with an identity link function and normally distributed errors. Data will be presented as the unadjusted absolute difference between the groups along with 95% confidence intervals.

2) *Proportion of patients achieving optimal adherence* (defined by ≥ 0.80 PDC): This outcome will be compared using generalized estimating equations with a logit link and binary distributed errors. Data will be presented as the unadjusted odds ratio for optimal adherence between the groups along with 95% confidence intervals.

Secondary analyses:

Healthcare resource utilization and spending: Secondary analyses of healthcare resource utilization will use a similar approach as the primary analysis among the full analysis set, except that we will use log link functions with Poisson errors to describe the count data. Health spending will also be evaluated with variances proportional to the mean (e.g., Poisson-like errors) using log-link functions in generalized estimating equations, which has been found to describe insurer healthcare spending data accurately based on prior research.⁵ Data will be presented as the unadjusted odds ratio along with 95% confidence intervals.

Adjusted analyses: If there are differences in baseline characteristics between study groups that are believed to be confounders (defined by a standardized mean difference of >0.1), we will repeat all of our analyses for the primary and secondary outcomes after adjusting for these covariates in multivariable regression. We will present these as adjusted effect estimates along with 95% confidence intervals.

Interactions: We will also explore any potential differences in effectiveness by the specific pharmacist delivering the intervention by evaluating effect measure modification and using interaction terms within the main model for the primary outcome of change in HbA1c. We will present p-values for interactions.

Subgroups: Subgroup analyses of the primary outcome (change in HbA1c) will also be performed for key subgroups, according to age, sex, depression, and baseline medication adherence levels. These analyses will be performed separately among subgroups of the characteristics and compared between the treatment arms. Data will be presented as unadjusted absolute differences in the change in HbA1c along with 95% confidence intervals.

Sensitivity analyses:

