For the glycemic control outcomes, we will also conduct a complete case analysis among patients with complete HbA1c follow-up data. We will also repeat our analyses with longitudinal modeling methods in generalized estimating equations that incorporate any additional HbA1c laboratory values in the 12-month follow-up period, for both the primary outcome of change in HbA1c and secondary outcome of the proportion achieving optimal control.

4.2.2 Secondary objective (Prediction modelling):

Overview

As a secondary aim, we will use predictive analytic approaches to examine whether the clinical outcomes could have been predicted based on patient factors, such as sociodemographic, clinical, medication use and receipt of the pharmacist-delivered telephonic intervention. The goal is also to identify patients who were most likely to respond to this type of intervention. In this aim, we will retrospectively examine whether these characteristics predict glucose control (e.g., HbA1c $<8\%$) and medication adherence (e.g., PDC ≥ 0.80). Specifically, we will evaluate prediction models with respect to their ability to discriminate and explain variation between patients who did and did not meet the glycemic and medication adherence targets during the follow-up period.

Model definitions:

To assess the ability to predict patients who will respond to the intervention, for each outcome (e.g., HbA1c $<8\%$ and PDC ≥ 0.80), we will develop and estimate a series of logistic regression models for patients in both the treatment and control groups, incorporating different patient characteristics

(described in 4.2.1) as predictors. We will model these particular outcomes because these are considered to be clinically meaningful cut-points for achieving optimal control for diabetes and adherence, respectively, and will be meaningful measures for providers, policymakers, and payers alike. For these models, the outcome will be treatment response as defined by each outcome and will include different numbers of predictor variables, in a method similar to previous work.^{16,17} As predictors in these models, we will incorporate patients' baseline demographic, clinical, and resource utilization characteristics.

Model estimation and validation:

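### The HbA1c <8.0% secondary outcome is tested with an unadjusted odds ratio that leaves out baseline HbA1c; pre-specifying it as a covariate is a free, modest gain in precision

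*SAP*

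**What the plan says.** - **Entry.** SAP 1.2 requires an HbA1c of at least 8% within the previous six months: "If patients had multiple HbA1c lab values, the latest value was evaluated". No second qualifying value is needed. Protocol Table 1 has the same threshold and window.
- **Outcome.** SAP 3.2: "Optimal glycemic control will be defined as the proportion of patients who achieved an HbA1c result <8.0% in the 12-month follow-up period". It then settles which result counts; the analysis "will use the HbA1c result recorded closest to the 12-month end of follow-up for the primary analysis". Missing follow-up values are multiply imputed, and the SAP adds: "This outcome will be analysed formally". The cut-off is justified by guidelines and health-plan measures: "This conservative threshold is based on the minimum threshold that nearly all patients should achieve".
- **Analysis.** SAP 4.2.1 uses generalised estimating equations with a logit link: "Data will be presented as the unadjusted odds ratio for optimal glycemic control between the groups along with 95% confidence intervals".
- **Adjustment.** This is conditional. If characteristics believed to be confounders differ by a standardised difference above 0.1, "we will repeat all of our analyses for the primary and secondary outcomes after adjusting for these covariates in multivariable regression". The baseline characteristics named in SAP 4.2.1 cover demographics, comorbidities, drug class, baseline PDC, brand status, copayment and utilisation, but not HbA1c.
- **Sensitivity analysis.** A longitudinal model, which also covers this outcome, will "incorporate any additional HbA1c laboratory values in the 12-month follow-up period".
- **Availability.** SAP 3.1 notes that every included patient has a baseline HbA1c.

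**The concern.** Entry is at or above 8% and success is below 8.0%, so distance from the line at baseline largely determines who can cross it. A patient entering at 8.0 needs a fall of 0.1; a patient entering at 11 needs more than 3 points. The planned odds ratio treats the two alike. The primary outcome at least subtracts the baseline value, whereas this outcome makes no use of it.

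Two things are at stake. The first is precision in a formally tested secondary outcome. The second is interpretation. Patients chosen on a high reading tend to read lower next time, so some in each arm will fall below 8.0% without any programme effect. The results are meant for payers and providers (Protocol 8.1), who could take an arm's percentage in control as the share the programme helped.

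**Working it through.** **1. The plan's own figures.** Neither document gives a rate, effect size or power for the <8.0% outcome. Protocol Table 5 concerns mean HbA1c only, and it reproduces: 2 × (1.960 + 0.842)² × 1.9² / 0.5² = 227 per group (228 by t-test); 228 × 1.03 = 235; 235 / 0.75 / 0.45 = 696. It says nothing about the binary outcome.

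**2. Would the conditional rule bring baseline HbA1c in?** Suppose it were among the characteristics screened. With 700 per arm, the standard error of a standardised difference under randomisation is √(2/700) = 0.0535. The trigger of 0.1 is then 0.1 / 0.0535 = 1.87 standard errors, which is exceeded by chance about 6% of the time. So in about 94 of 100 such trials no adjusted analysis would include it, even if it were listed.

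**3. What does leaving it out cost?** Inputs from the documents:
- selection on one value ≥8.0, success on one later value <8.0 (SAP 1.2, 3.2);
- 700 per arm with 25% loss, so 700 × 0.75 = 525 per arm (SAP 1.3);
- two-sided alpha 0.05 (SAP 1.3, 4.1).

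Assumed inputs, which the documents do not give:
- normally distributed true HbA1c;
- visit-to-visit SD 0.3 to 0.8;
- real 12-month drift with SD 0 to 1.5;
- an overall shift of 0.25 points. For orientation, the plan's 0.5 confined to participants would average 0.45 × 0.5 = 0.225 over the arm at the Protocol's 45% rate, and 0.30 × 0.5 = 0.15 at the SAP's 30%.

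Each simulated trial was analysed by logistic regression on arm alone, then on arm plus baseline HbA1c.

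| Quantity | Arm only | Arm + baseline HbA1c |
|---|---|---|
| Power, range over scenarios | 0.39-0.99 | 0.40-1.00 |
| Mean z | reference | about 4-18% higher |
| Type I error | near nominal | near nominal |

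The gain is largest when visit noise and drift are small, so that baseline predicts follow-up well, and smallest when drift is large. Since z grows with the square root of sample size, it corresponds to 1.04² = 1.08 up to 1.18² = 1.39, or roughly 8-39% more patients. These are complete-data simulations; the planned multiple imputation was not modelled.

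**4. Is the unadjusted test biased?** No. With no effect and 525 per arm, 4,000 simulated trials per setting gave type I error of 0.053 to 0.058 (Monte Carlo standard error about 0.0035). Noise and regression to the mean act equally, in expectation, on both randomised arms.

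**The case against.** The strongest reply is that nothing in the planned inference is wrong. The comparison is randomised, the estimand is a between-arm odds ratio, the cut-off is a recognised quality measure, and the size of change is already the primary outcome. Counting 8.0 to 7.9 as success is a property of any threshold. The plan also has a conditional adjusted analysis and a longitudinal sensitivity analysis. All of this stands. It limits the point to efficiency and interpretation, and it supports keeping the <8.0% outcome. It does not answer the omission: imbalance is not the reason to adjust for a strong predictor, and the longitudinal model adds follow-up values without specifying a baseline covariate.

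Stronger readings that the documents do not support:

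- **Any one value below 8.0% during the year counts.** The definition sentence alone might suggest this, but SAP 3.2 goes on to fix the result nearest month 12. The distinction matters. With an assumed underlying mean of 7.5, SD 1.9, visit SD 0.5 and no effect, 14.6% fall below 8.0% on one value, against 29.1% on any of four.
- **A known share of those in control is noise.** A reader might infer, say, 5-31%. That depends on inputs the documents lack. Keeping the overall SD between 1.0 and 1.9 (the Protocol's range is 1.0 to 2.0), with assumed mean 7 to 9 and visit SD 0.2 to 0.9, gives anything from about 3% to 75%.
- **A required fall of 0.5 points would isolate real improvement.** Regression to the mean produces such falls by itself. In simulated patients with no effect who end below 8.0%, 82% had already fallen that far at visit SD 0.5, and 86-95% had with drift. The rule adds almost no power, and the plan's 0.5 (SAP 1.3) is an average between-group difference, not an individual threshold.

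**Conclusion.** The point holds as a minor one. The planned test of the <8.0% outcome is valid, but it leaves out a predictor that every patient has and that the conditional rule would seldom, if ever, bring in. Under the stated assumptions, including it raises the mean z by about 4-18%; in some scenarios power barely changes. The range depends on the assumed visit-to-visit SD, drift and 0.25-point shift. The direction is what one expects of a prognostic baseline covariate in a randomised comparison. Regression to the mean contributes to the proportion in control in both arms, so neither arm's percentage measures patients improved by the programme; only the contrast between arms bears on its effect.

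**What to change.** In SAP 4.2.1, keep HbA1c <8.0% at the value nearest month 12 as the outcome and:

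1. Pre-specify baseline HbA1c as a covariate in the logistic GEE, whatever the observed imbalance.
2. Report the standardised difference in proportions with its 95% CI beside the odds ratio: average the model's predicted probabilities over all patients under each assignment, within each imputed data set, then combine.
3. State that arm-level percentages describe status at follow-up, not patients improved by the programme.

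It would also help to align the SAP 3.2 definition sentence with the nearest-to-month-12 rule that follows it.

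The cost is SAP wording and a little programming; no new data are needed. The one downside is that the adjusted odds ratio is conditional on baseline HbA1c and so differs in meaning from the unadjusted one; the standardised difference addresses this. The change should be dated before the investigators receive the outcome data, which SAP 2.2 places after the lock in late March 2018.

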- 3) Loss-to-follow-up: Due to the potential for patients changing insurances particularly at the end of the calendar year, we anticipate that there could be some non-differential loss-to-follow-up of patients in the study. There may also be patients who do not have follow-up A1cs, despite restricting to patients whose providers have at-risk contracts with Horizon BCBS.
- 4) Pharmacist contact rate: We anticipate that approximately 45% of the patients will be reached by the pharmacists delivering the intervention.

Table 6. Justification: Adherence power calculation parameters and ranges

Range of parameters: input ranges	Difference in mean PDC: 5% Sample size (N range)/group
Baseline adherence: 50% --> N ₁	253
Intra-cluster correlation (N ₂ =N ₁ *1.03)	261
Loss-to-follow-up (LTF): 10-25% (N ₃ =N ₂ /[1-rate])	(best case: 290, worst case: 347)
Pharmacist contact rate: 35-50% (N ₄ =N ₃ /rate)	(best case: 580, worst case: 993)
Total	45% reach rate and 15% LTF: 682 patients/arm

[figure not shown]
Power (1-β): 0.80; Alpha (α): 0.05

Explanation of additional study parameters – Secondary outcome (Adherence)

- 1) Baseline adherence:
 - o 5% absolute difference in mean PDC has been seen in previous intervention studies and is considered to be a clinically meaningful difference^{16,24}
 - o Assuming ~50% baseline adherence based on previous literature²⁴
- 2) Loss-to-follow-up: Due to the potential for patients changing insurances, we anticipate there could be some non-differential loss-to-follow-up of patients in the study. Prescription claims will be captured on all patients included in the study by definition, enabling the calculation of adherence until loss of continuous eligibility.

Clinical Study Protocol
Drug Substance NA
Study Code D1843R00254
Edition 2
Date

Figure 3. Schematic of analytic plan

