1.3 Number of subjects

In total, 1,400 subjects were randomized in a 1:1 ratio to the intervention or control group. Our study was designed to be sufficiently powered to detect small but clinically meaningful changes in the primary outcome of HbA1c change.

We considered the following assumptions in the power calculations. Assuming that 30% of study subjects in the intervention arm agree to participate in the intervention, we randomized 700 individuals

to each of the intervention and control groups in order to achieve 80% power to detect an average change in HbA1c of 0.5% between the intervention and control groups at an alpha threshold of 0.05 with a HbA1c standard deviation=1.9 (the most commonly cited value in the literature for HbA1c), accounting for 25% rate of loss-to-follow-up.^{1,2} We used Proc Power in SAS 9.4 (Cary, NC) using a t-test and adjusted the sample size to account for the reach rate. Because patients may change insurance, in particular at the end of the calendar year, we accounted for a rate of non-differential loss-to-follow-up of 25% rate. There may also be patients who do not have follow-up HbA1cs, despite restricting to patients whose providers have at-risk contracts with Horizon Blue Cross Blue Shield. As described later in Section 3, we will use multiple imputation methods to account for patients with no follow-up HbA1c values. In addition, this proportion of patients who agree to participate in this intervention has been observed in prior studies that have used a similar approach.²⁵ Finally, the proposed difference of HbA1c of 0.5% is the level that clinical guidelines consider to be a clinically meaningful difference in glycemic control. This HbA1c difference has also been observed in prior work with clinical pharmacists.⁸ Because the primary outcome is HbA1c change, we expect to see clinically meaningful differences in these levels within the 11 to 12-month follow-up period.^{3,4}

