For secondary outcomes, with this sample size, we will also have the power to detect at least a 4% absolute difference in adherence (i.e., mean PDC levels) between the intervention and control groups, assuming baseline rates of adherence of 50%. We used Proc Power in SAS 9.4 (Cary, NC) using a chi-square test and adjusted the sample size to account for the reach rate. These differences in adherence have been observed as meaningful in prior research, and the baseline rate of adherence is based on prior research in this field.⁵⁻⁷ In addition, prescription claims will be captured on all patients included in the study by definition for inclusion, enabling the calculation of adherence in the follow-up period until loss of continuous eligibility. Therefore, there is no substantial lost-to-follow up expected for this outcome.

Finally, for the secondary objective (Aim 2), this sample size would also provide enough patients for the predictive modelling, given the relative non-rare nature of the study outcomes (glycemic control and medication adherence) and number of predictors considered per number of patients in the study.⁸

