2.2 Violations and deviations

We have not identified any important protocol deviations in this study to date. To our knowledge, no patients were erroneously randomized (in that they did not actually meet inclusion or exclusion criteria at the time of randomization). In other words, at the time the assignment was actually performed in Oct 2016 and Dec 2016, all patients were eligible for the study.

However, once the database lockout for follow-up outcomes is complete (late March 2018), Horizon will be sharing the full data, including prescription claims, medical claims, enrolment files, and laboratory values, to the [REDACTED] investigators for study analysis. Once these data are cleaned and the analytic dataset is generated, it is possible that a few patients may appear to have been erroneously randomized because there may have been new lab values provided to Horizon that were not actually available to Horizon at the time the allocation was performed. In addition, because of the minor lag between pulling the data, evaluating eligibility in insurer claims data, and the subsequent randomization done by Horizon, it is possible that a small percentage of individuals may have terminated their medical or prescription drug benefits and could no longer be eligible.

Based on prior studies of insurance trials conducted in claims data, we anticipate that no more than 5% of patients may be subject to any protocol deviations related to insurance data lag or adjudication.^{4,5,9} Moreover, we do not expect that there will be any differential deviations between the two study arms, so the study results should be unbiased. Regardless, patients who are found to have not met these enrolment criteria once the data is received will not be included in either of the Analysis Sets. Similarly, in the rare case that patients are found to have randomized multiple times or if there were any other unanticipated deviations, they will not be included in the Analysis Sets. We do not expect any of these potential deviations to affect the validity of the study results as they are not expected to be differential between the study arms.⁹

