3.3 Secondary outcome (two medication adherence outcomes):

Medication adherence will be measured using filling patterns in pharmacy claims data for medications that qualified a patient for inclusion in the study.¹³ For each medication, we will create a drug supply diary linking all observed fills after initiation based on dispensing date and days' supply. Different drugs in the same chemically-related therapeutic class (e.g., sulfonylureas) will be considered to be interchangeable. We will allow for up to 180 days of carryover supply. From these supply diaries, we will calculate the proportion of days that patients had medications available to them, or the proportion of days covered (PDC), by dividing the number of days with medication available by the number of days during follow-up.¹⁴ If a patient loses continuous eligibility during the year after the index date, the PDC will be calculated based on the number of days available. If a patient loses continuous eligibility during the year after the index date, they will be censored on that date, and the PDC will be calculated based on the number of days available. In this PDC measurement, if patients had at least one antidiabetic medication available, then they will be considered to be adherent for that day. This definition allows for outcome measurement even when patients switch (e.g., switch from metformin to a sulfonylurea) or intensify therapy (e.g., adding a second oral diabetes medication or injectable medication).

Using this PDC measure, we will observe *1) the mean PDC in each study arm* and *2) the proportion of patients achieving optimal adherence* (defined by ≥ 0.80 PDC) as adherence outcomes in the follow-up period. In a sensitivity analysis of this outcome, medication adherence will be measured by calculating the PDC beginning from the first fill of a medication after assignment until the end of the 12-month follow-up. There will be no missing data for these outcomes, as previously described.

These outcomes will be analysed formally.

3.4 Secondary analyses:

Resource utilization:

As secondary analyses, we will also measure healthcare spending and healthcare resource utilization, including outpatient visits, emergency room visits, and hospitalizations, in the follow-up period in the medical and pharmacy claims data. Healthcare spending will be measured as total allowed amounts in

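### The SAP drops the protocol's loss allowance for adherence although pharmacy claims end with coverage, so leavers' PDC comes from short windows that count as much as a full year

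*SAP*

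**What the plan says.** SAP 1.3 gives the reason for HbA1c loss ("Because patients may change insurance, in particular at the end of the calendar year") and the rate ("we accounted for a rate of non-differential loss-to-follow-up of 25% rate"). For adherence it argues that claims are captured on everyone until eligibility ends, and concludes: "Therefore, there is no substantial lost-to-follow up expected for this outcome". SAP 3.3 repeats the idea: "There will be no missing data for these outcomes, as previously described".

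SAP 3.3 also states the rule for leavers: they are censored at loss of eligibility, and PDC is calculated on the days they have. It sets no minimum window. The models for both PDC outcomes in SAP 4.2.1 state no weight or exposure term. The one PDC sensitivity analysis means "calculating the PDC beginning from the first fill of a medication after assignment until the end of the 12-month follow-up".

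Protocol 8.2 offers nearly the same argument about claims capture but still budgets for loss. Table 6 gives a range of 10-25% and ends at "45% reach rate and 15% LTF: 682 patients/arm". SAP section 6 lists no changes from the protocol.

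On timing, "Follow-up will begin from the date of treatment group assignment" (SAP 3.1), and SAP 2.2 dates eligibility "at the time the assignment was actually performed in Oct 2016 and Dec 2016".

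**The concern.** A patient who changes insurer disappears from the pharmacy claims as well as from the laboratory feed. The SAP plans for this in the primary outcome, with multiple imputation and a complete-case check, but treats adherence as nearly immune. Being able to calculate a PDC for each patient is not the same as observing 12-month adherence.

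Over two or four weeks, PDC depends largely on whether one fill falls inside the window. Such values pile up near 0 and 1, yet each carries full weight in the mean and in the proportion at or above 0.80. Protocol 4.2 plans first contact within the first month, so the earliest leavers may have had little or no intervention. Improved adherence is part of the stated primary objective and both PDC outcomes are to be analysed formally, so the precision claimed for them should rest on a stated loss assumption.

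**Working it through.** **1. Reproduce Table 6.** Inputs: 5-point difference, two-sided alpha 0.05, power 0.80. The SD is not stated. A t-test with SD 0.20 gives 253 per group, so 0.20 is the implied SD. Then:
- clustering: 253 × 1.03 = 261
- 15% loss: 261 / 0.85 = 307
- 45% reach: 307 / 0.45 = 682 per arm, as printed.

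**2. Change only the loss.** At 25%, the top of Table 6's range: 261 / 0.75 = 348, and 348 / 0.45 = 773 per arm, against 700 randomized.

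**3. Restate the SAP's detectable difference.** SAP 1.3 claims 4 points. Discounting N for loss as Table 6 does multiplies the detectable difference by 1/√(1 − loss):
- 15%: 4.0 / √0.85 = 4.3 points
- 25%: 4.0 / √0.75 = 4.6 points

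The 4-point starting value is taken as stated. How it was derived is a separate question.

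**4. Patients and windows.** 15% of 1,400 is 210 patients; 25% is 350. Counting days from assignment to 31 December 2016 inclusive:
- assigned 1-31 October: 92 down to 62 days
- assigned 1-31 December: 31 down to 1 day

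Twelve months from either wave contains only one year-end that shortens follow-up materially, and this is it.

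**5. Effect of short windows.** A refill simulation used assumptions that are mine except for the 0.50 mean: true mean PDC 0.50 or 0.65, between-patient SD 0.20 or 0.25, 30- or 90-day fills, random gaps, 6,000 patients per scenario, and the same behaviour in leavers and stayers. Ranges are across scenarios.

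| Window | Share with PDC ≥0.80 | Status at 0.80 differs from 365-day status |
|---|---|---|
| 365 days | 0.10-0.41 | – |
| 91 days | 0.16-0.52 | 10-24% |
| 30 days | 0.33-0.59 | 24-34% |
| 15 days | 0.42-0.62 | 30-38% |

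Mean PDC hardly moves. Its SD is 0.35-0.45 over 30 days against 0.22-0.28 over 365 days.

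**6. Effect on the whole sample, if all 25% leave at one early time.** The SD of PDC rises by a factor of 1.03-1.15 (75 days), 1.10-1.24 (30 days) or 1.16-1.30 (15 days). With 30-day windows, the overall share at or above 0.80 moves, for example, from 0.097 to 0.156, or from 0.373 to 0.411. In one scenario (mean 0.50, 30-day fills, 30-day window), power at 700 per arm for a 3-point difference falls from 0.72 to 0.56.

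A second set of assumptions (Beta(4,4) adherence, 30-day fills, exponential gaps, 12-month SD 0.19) gives variance ratios of 1.24, 1.64 and 1.98 for 75, 30 and 15 days. As SD factors these are √1.24 = 1.11, √1.64 = 1.28 and √1.98 = 1.41.

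**The case against.** The SAP discloses the truncation: it says adherence is calculable only until eligibility ends, and that leavers are censored. If the outcome is adherence while enrolled, every patient with an eligible day has a value. A reader might infer that the no-missing-data statement is false. Under that definition it is literally true of the main analysis, and the defect is what it leaves unsaid. It does not extend cleanly to the first-fill sensitivity analysis, where a patient with no post-assignment fill has no start date.

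A reader might also carry the full 25% over to adherence. The documents do not establish that. The protocol's HbA1c loss item also covers patients without a follow-up result, and the protocol uses a lower figure for adherence. That figure is 15%, however, and not zero.

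Nor is there a case for multiplying the required sample size by 2.2 to 3.5. Those figures come from dividing the variance ratios 1.24 to 1.98 by 0.75², which requires every leaver to share one short window and to show no effect at all. The SAP says loss occurs particularly at year-end, not only then. October assignees leaving at year-end have at least 62 days, so 15- or 30-day windows for all leavers would require them all to be December assignees. With contact planned in the first month, a 75-day leaver may have had weeks of intervention.

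Extra variance alone does not overturn the 4-point claim. With SD 0.20 and 700 per arm, power for 4 points is 0.96. It becomes about 0.92, 0.83 or 0.76 with variance multiplied by 1.24, 1.64 or 1.98.

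Finally, enrolled days are a post-randomization variable. Weighting the main analysis by them would depart from an equal-weight comparison of all assigned patients. That objection stands.

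**Conclusion.** The inconsistency is real and should be corrected. The SAP removes the protocol's 15% adherence allowance without recording a change, while attributing 25% loss for HbA1c to a cause that also ends pharmacy claims. Truncated windows then receive full weight, and no planned analysis examines early leavers. The first-fill analysis shortens their windows further.

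The stated detectable difference moves from 4.0 to about 4.3-4.6 points. The rise in SD, by 1.03-1.30 or up to about 1.4 at 15 days, is an upper bound because it assumes that all 25% leave early. The actual size depends on the split between waves and on exit dates, which the documents do not give.

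A reader might infer that the adherence comparison is biased between arms. The documents do not support that: loss is assumed equal, and under equal loss the consequences are noise, dilution and misclassification at 0.80. Equality is an assumption, which is why enrolled days should be reported by arm. The primary HbA1c analysis is unaffected.

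**What to change.** 1. Reword SAP 1.3 and 3.3 to say that PDC is calculable for all patients with eligible days but truncated for those who disenrol. Restore the adherence loss allowance of 15% (range 10-25%), restate the detectable difference as in steps 2-3, or record and justify the departure in section 6.
2. Keep the unweighted intention-to-treat PDC analysis as the main one. Report enrolled days by arm. Prespecify two sensitivity analyses: covered days over enrolled days, weighted by enrolled days; and patients enrolled for the full 12 months.
3. State how patients with no post-assignment fill enter the first-fill sensitivity analysis, for example with PDC 0, so that they are not dropped.

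This costs SAP wording and a few extra model runs. No new data are needed, since the enrolment files are already to be shared for analysis. The price is a less favourable stated detectable difference, and sensitivity analyses that lean towards patients who stay insured.
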